Table 8. Identity of Investigational Medicinal Products (Cohort 3)

Investigational medicinal product	Pharmaceutical form	II)ASA	Route of administration	Manufacturer
ATL-001	Liquid syrup	1 mg/kg	Oral	Polypeptide Therapeutic Solutions
Placebo	Liquid syrup	Not applicable	Oral	Polypeptide Therapeutic Solutions

Table 9. Identity of Investigational Medicinal Products (Cohort 4)

Investigational medicinal product	Pharmaceutical form	II)ASA	Route of administration	Manufacturer
ATL-001	Liquid syrup	2 mg/kg	Oral	Polypeptide Therapeutic Solutions
Placebo	Liquid syrup	Not applicable	Oral	Polypeptide Therapeutic Solutions

Table 10. Identity of Investigational Medicinal Products (Cohort 5)

	Pharmaceutical form	II)nea	Route of administration	Manufacturer
ATL-001	Liquid syrup	4 mg/kg	Oral	Recipharm
Placebo	Liquid syrup	Not applicable	Oral	Recipharm

10.1.2 Packaging and Labelling of Investigational Medicinal Product(s)

The Sponsor will supply the study medication labelled and packaged for this study.

All packaging and labelling as well as the production of study medication will be in accordance with EudraLex volume 4, Annex 13 "Good manufacturing practices for Medicinal products for human and veterinary use" and applicable local regulatory requirements.

10.1.3 Storage and Handling of Investigational Medicinal Product(s)

Only subjects enrolled in the study may receive the IMP and only authorized site staff may supply the IMP. The IMP supplies must be stored in a secure, environmentally controlled, and monitored (manual or automated) area in accordance with the labelled storage conditions with access limited to the investigator and authorized site staff.

Date: 13 December 2023

Sponsor: Atlas Molecular Pharma S.L. Study Code: ATL001-PI-CEP

NCT No.: 05647343

The Investigator and study staff must adhere to Good Clinical Practice (GCP) guidelines, as well as local or regional requirements. Under no circumstances will the Investigator allow the IMP to be used other than as directed by this protocol.

Further guidance and information for the final disposition of unused study interventions are provided in the Pharmacy Manual.

The IMPs must be received by a designated person at the study site, handled and stored safely and properly, and kept in a secured location to which only the designated personnel have access. Upon arrival of IMPs at the site, site personnel should check for damage and verify proper identity, quantity, integrity of seals and temperature conditions, and report any deviations or product complaints to the Clinical Trial Monitor upon discovery. Upon receipt, all IMPs must be stored according to the instructions specified on the labels. The recommended storage conditions for the IMP are between 2-8 °C. Clinical supplies are to be dispensed only in accordance with the protocol.

Refer to Pharmacy Manual with details on storage and handling of IMPs. Storage and use conditions will be also clearly detailed in a separated "Instruction for administration" document.

10.2 Method of Assigning Subjects to Treatment Groups

At each investigated cohort, subjects will be randomized in the ratio of 6 active treatments to 2 placebos (3:1). For safety reasons, the subjects of each cohort will be divided in 2 sub-cohorts with 2 sentinel subjects in the first sub-cohort and 6 additional subjects in the second sub-cohort (see Section 8.1). The randomization schedule will be designed so that in each sub-cohort there will be 1 subject scheduled to receive placebo.

The randomization list will be performed by someone not directly enrolled in the research team. SAS software version 9.4 or higher will be used. The disclosure of the randomization schedule will be done at the end of the study or in case it is needed to provide convenient medical care to any subject due to AEs.

Following confirmation of eligibility, subjects will be assigned a subject randomization number at Baseline using an Interactive Response Technology (IRT) system in the order in which they are randomized in the study.

Only subjects receiving an IMP administration will receive a randomization number. Subjects who replace a discontinued subject will receive the same administration as the discontinued subject. This subject will receive a number that refers to the number of the subject that is being replaced.

In order to maintain the double-blind study, the administration of the IMP must occur individually and separately, and in the absence of the physician responsible for the study. This is because the reaction after its administration could be easily distinguishable between placebo and IMP.

10.3 Dose and Treatment Regimens in the Study

The IMPs will be administered orally once daily for 5 days (i.e., total of 5 administrations of IMP). On the morning of Day 1 to Day 5, each subject will receive a single oral dose of ATL-001 or placebo administered under fasting conditions as described above (Section 8.1). Subjects will fast overnight (at least 10 hours) prior to be dosed at approximately the same time on the morning of Day 1 through Day 5.

The first and last administration of the IMP (Day 1 and Day 5) will be performed at the hospital. At Day 2, prior to all clinical activities and assessments and to hospital discharge, the subject will be administered with the IMP. The other days (Day 3 to Day 4), treatment will be self-administered at home. During the first hospital admission (Day 1 to Day 2), subjects will be provided with the IMP to be administered daily from Day 3 to Day 4 and they will receive detailed instructions on how to properly take and storage the medication.

The starting dose in the Cohort 1 will be 0.2 mg/kg of ATL-001 or placebo. The doses in Cohort 2, Cohort 3, Cohort 4 and Cohort 5 are planned to be 0.5 mg/kg, 1 mg/kg, 2 mg/kg and 4 mg/kg of ATL-001 or placebo. These doses were selected based on pre-clinical data. Dose selection rationale is detailed in Section 6.3. ATL-001 dose to be administered from Day 1 to Day 5 should be calculated based on the subject's weight assessed at Screening visit.

Upon consideration of all the available safety and tolerability data from all cohorts tested to date, the DSMB will provide recommendation for the progression to the next cohort or may recommend an

Date: 13 December 2023

Sponsor: Atlas Molecular Pharma S.L. Study Code: ATL001-PI-CEP

NCT No.: 05647343

additional procedure to be taken (i.e., to test a different IMP dose or administration schedule), as outlined in Section 8.1.1.

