8.2 Study Procedures

8.2.1 Schedule of Study Events

The study assessments described in the sections below are presented in detail in Section 11.2 (PK assessments), Section 11.3 (demographic data and baseline characteristics) and Section 11.4 (safety assessments). Recording and reporting of AEs are described in detail in Section 12.

The timing of all study events is shown in Table 1.

The following points must be noted:

- If different assessments are scheduled for the same nominal time, then the assessments should occur in the following order whenever possible:
 - 1. 12-lead ECG and vital signs
 - 2. Blood draw
- The timing and number of planned study assessments, including safety or PK assessments may be altered during the course of the study based on newly available data (e.g., data from preceding cohorts) after DSMB recommendation (see Section 8.1.1).
- Any change in the timing or the addition of time points for any planned study assessment must be documented in a Note to File, which must be approved by the relevant Sponsor study team member and will be archived in the study Sponsor and site study files. This will not constitute a protocol amendment.

The day of the first administration of the IMP will be considered Day 1 of the study.

Version: 4.0

Date: 13 December 2023

Sponsor: Atlas Molecular Pharma S.L. Study Code: ATL001-PI-CEP

NCT No.: 05647343

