8.2.1.2.1 Hospital admission (Day 1 to Day 2)

8.2.1.2.1.1 Day 1 (Baseline)

At Day 1 (Baseline), the following activities and assessments will be performed prior to IMP administration:

- Assessment of changes in inclusion/exclusion criteria
- Randomization
- Assessment of changes in the medical history
- Physical examination
- Vital signs, including blood pressure, pulse rate and body temperature
- Laboratory safety assessments, including hematology, biochemistry and urinalysis
- Drug of abuse and alcohol screen
- Urine pregnancy test (for female subjects of childbearing potential only)
- ECG
- PK blood sampling (0 min or pre-dose).

Version: 4.0

Date: 13 December 2023 NCT No.: 05647343

Concomitant medications

AEs (pre-treatment-emergent events)

After performing all the previous assessments, the IMP will be administered and the subjects will remain in the hospital for 24 hours. During Day 1, the following additional activities and assessments will be performed:

Sponsor: Atlas Molecular Pharma S.L.

Study Code: ATL001-PI-CEP

- Physical examination (2 hours after the first IMP dose)
- Vital signs, including blood pressure, pulse rate and body temperature (2 hours after the first IMP dose)
- Laboratory safety assessments, including hematology, biochemistry and urinalysis (2 hours after the first IMP dose)
- ECG (2 hours after the first IMP dose)
- PK blood sampling (15 min, 30 min, 1 hour, 1:30 hours, 2 hours, 2:30 hours, 3 hours, 4 hours, 6 hours, 8 hours and 12 hours after the first IMP dose)
- Concomitant medications
- AEs

8.2.1.2.1.2 Day 2

Subjects will be discharged at Day 2 after completing their assessments and after receiving the IMP. At Day 2 (24 hours after the first IMP dose), the following activities and assessments will be performed:

- Physical examination
- Vital signs, including blood pressure, pulse rate and body temperature
- Laboratory safety assessments, including hematology, biochemistry and urinalysis
- ECG
- PK blood sampling
- Concomitant medications
- AEs

Prior to hospital discharge (and after the performance of the activities and assessments listed above), the subjects will be administered with the IMP.

8.2.1.2.1.3 Day 3 to Day 4

Treatment will be self-administered at home once daily following the investigator instructions. No site visits are planned from Day 3 to Day 4. During this period of time, subjects will record daily AEs and IMP administrations in the subject diary.

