11.2.1 Sampling Procedures

Blood samples will be collected at specific time points throughout the study. The maximum amount of blood to be collected for PK analyses along the study is 5 mL in each extraction point. For each day when a PK sampling is collected a total amount 60 mL of blood (12 points) will be withdrawn.

The timing of the sampling is described in Section 8.2.1 and Table 1.

Details on collection, storage and handling of blood samples will be included in the respective Laboratory Manual.

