13.1.5.1 Pharmacokinetic Analysis

ATL-001 plasma concentration data will be listed by treatment, subject and visit/sampling time point. Descriptive summary statistics will be provided by treatment, and visit/sampling time point, including the frequency (n, %) of concentrations below the limit of quantification and reported as zero.

Summary statistics will include mean (arithmetic and geometric), standard deviation, coefficient of variation (arithmetic and geometric), median, minimum, and maximum. An exception to this is t_{max} where median, minimum and maximum will be presented. Concentrations below limit of quantification will be treated as zero in summary statistics and for PK parameter calculations. A geometric mean will not be reported if the data set includes zero values. The PK data of all subjects who received at least one dose of ATL-001 and who have at least one valid PK measurement will be used in the PK set analysis.

A non-compartmental analysis will be used to calculate the PK parameters detailed on Section 11.2. A normalization by dose will be performed in the main PK parameters ($AUC_{(0-t)}$ and C_{max}).

Unassessable subjects for the PK analysis are:

Version: 4.0

Date: 13 December 2023

Sponsor: Atlas Molecular Pharma S.L. Study Code: ATL001-PI-CEP

NCT No.: 05647343

• Subjects who experienced an AE (e.g., vomiting) and took (or not) concomitant medication, if the experienced AE itself and/or the concomitant medication taken, interferes in a relevant manner with his PK results

- Subjects missing more than four samples throughout the study period.
- Excessive deviation between consecutive blood samples collection from scheduled time of sample collection (more than 10% of the time period between consecutive samplings)
- Subjects with lack of any measurable concentration or only very low plasma concentration for drug product*
- Subjects with non-zero baseline concentration > 5% of C_{max}*
- Subjects with less than three quantifiable concentrations*

*Except for these criteria, decision to exclude a subject from the statistical or PK analysis must be made before bioanalysis and has to be properly documented.

More details on the PK parameters, analysis and presentation of study results will be provided in the PK analyses SAP.

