4.6 Pharmacokinetic Endpoints

Blood samples are collected at pre-dose 0 hr and post-dose time points at 15 min, 30 min, 1 hr, 1.5 hr, 2 hr, 2.5 hr, 3 hr, 4 hr, 6 hr, 8 hr, 12 hr, and 24 hr on Day 1 and Day 5. To assess the PK profile of ATL001 after administration of multiple doses, the following PK parameters will be calculated using non-compartmental analysis (NCA) method with Phoenix® WinNonlin® software (Version 8.1 or higher, Certara, L.P.).

| Parameter | Definition |
|---|---|
| Day 1 (Initial Dose) | |
| C_{max} | Maximum observed plasma ATL-001 concentration, determined directly from individual concentration-time data |
| t_{max} | Time until C_{max} is reached, determined directly from individual concentration-time data |
| AUC_{0-last} | Area under the plasma ATL-001 concentration-time curve from time 0 to the time of the last detectable concentration after the initial dose, before the next dose administration |
| AUC_{0-12} | Area under the plasma ATL-001 concentration-time curve from time 0 to 12 hours after the initial dose |
| AUC_{0-24} | Area under the plasma ATL-001 concentration-time curve from time 0 to 24 hours after the initial dose |
| Day 5 (Steady State after Multiple Doses) | |
| C_{max-ss} | C_{max} at steady state |
| T_{max-ss} | T_{max} at steady state |
| C_{min-ss} | C_{min} at steady state |
| AUC_{τ} | Area under the plasma ATL-001 concentration-time curve during one dosing interval at steady state |
| $AUC_{0-last,ss}$ | Area under the plasma ATL-001 concentration-time curve from time 0 to the time of the last detectable concentration at steady state |
| $t_{1/2}$ | Apparent terminal elimination half-life at steady state |
| CL_{ss}/F | Apparent systemic clearance at steady state |
| V_{ss}/F | Apparent volume of distribution at steady state |
| $R_{ac}(AUC)$ | Accumulation ratio based on AUC, defined as AUC_{τ}/AUC_{0-24} |
| $R_{ac}(C_{max})$ | Accumulation ratio based on C_{max} , defined as C_{max-ss}/C_{max} |

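### Protocol Section 10.3 gives the Day 2 dose before the Day 2 assessments, against Section 8.2.1.2.1.2; if followed, the 24 h sample that closes Day 1 AUC0-24 is taken after dose 2

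*Protocol*

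**What the plan says.** Protocol Section 10.3 (Dose and Treatment Regimens) says "At Day 2, prior to all clinical activities and assessments and to hospital discharge, the subject will be administered with the IMP". The same section has subjects "dosed at approximately the same time on the morning of Day 1 through Day 5", which puts dose 2 at about 24 h after dose 1.

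Protocol Section 8.2.1.2.1.2 (Day 2) lists the assessments due 24 h after the first dose: physical examination, vital signs, laboratory tests, ECG, PK blood sampling, concomitant medications and AEs. It then says "Prior to hospital discharge (and after the performance of the activities and assessments listed above), the subjects will be administered with the IMP".

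On which text governs timing, Section 8.2.1 says "The timing of all study events is shown in Table 1", and Section 11.2.1 says "The timing of the sampling is described in Section 8.2.1 and Table 1".

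SAP Section 4.6 defines Day 1 AUC0-24 as "Area under the plasma ATL-001 concentration-time curve from time 0 to 24 hours after the initial dose", with no condition about dose 2. It does put that condition on Day 1 AUC0-last, which runs to the "last detectable concentration after the initial dose, before the next dose administration". Rac(AUC) is AUCtau on Day 5 divided by Day 1 AUC0-24.

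**The concern.** The two sections give opposite orders for the same morning, and no clause says which prevails. Section 10.3 is where dosing staff would naturally look for dosing instructions, so the wrong order could be carried out in good faith.

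If it is, the 24 h sample is no longer a pre-dose trough. It closes the 12 to 24 h trapezoid, the longest in the profile and half of the AUC0-24 interval. Drug from dose 2 can only add to that concentration. No dose is given on Day 6, so the Day 5 profile is clean and only the denominator of Rac(AUC) is inflated. Real accumulation could be hidden, or a ratio below 1 reported.

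Two further effects follow. The Day 2 ECG, vital signs and laboratory values become readings after dose 2, no longer comparable with Day 6. And Protocol Section 11.2 sends concentrations to the PK analyst after each cohort, for simulations that can inform the DSMB; these would be misled unless actual dose times are modelled.

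**Working it through.** **Which sentence is wrong.** The synopsis and Sections 8.1 and 8.2.1.2 say only that the Day 2 dose comes before discharge, so they do not settle the order. The schedule table (Protocol Table 1, SAP Section 2.3.5) has no dosing row. That leaves Section 10.3 against Section 8.2.1.2.1.2. Section 11.2.1 sends PK timing to Section 8.2.1, and the SAP's AUC0-last definition presumes that Day 1 sampling ends before dose 2. Both point to Section 10.3.

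**Would an existing rule catch the sample?**

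- Protocol Section 13.1.5.1 excludes for "Excessive deviation between consecutive blood samples collection from scheduled time of sample collection", above 10% of the interval between samples. For 12 to 24 h that is 0.10 × 12 h = 1.2 h = 72 min. A sample drawn on time at 24 h passes, whatever happened with dose 2.
- SAP Section 3.2 excludes subjects with major deviations that may have affected PK data, and Protocol Section 14.11 counts failures in giving study treatment as major. This removes the whole subject, and a site following Section 10.3 could say that it did not deviate.
- Individual profiles (SAP Section 5.4.4) could show an upturn at 24 h, but no action is attached.

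**Direction and size.** The plan has no figure to reproduce. I used a one-compartment oral model with unit dose and volume:

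C(x) = ka/(ka − ke) × [exp(−ke·x) − exp(−ka·x)], with ke = ln 2 / half-life.

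The sampling grid is the protocol's: 0, 0.25, 0.5, 1, 1.5, 2, 2.5, 3, 4, 6, 8, 12 and 24 h.

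*Worked case* (half-life 4 h, ka 2 per hour, no lag, sample 15 min after dose 2, linear trapezoid):

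- ke = 0.6931/4 = 0.1733 per hour. C(12) = 0.1369 and C(24) = 0.0171.
- Dose 2 adds C(0.25) = 1.0949 × (0.9576 − 0.6065) = 0.3844.
- Extra area = (12/2) × 0.3844 = 2.306.
- AUC0-24 goes from 5.931 to 8.237, a multiplier of 1.39.
- AUCtau on Day 5 = 6.034, so Rac(AUC) goes from 6.034/5.931 = 1.02 to 6.034/8.237 = 0.73.

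*Grid.* Half-life 1.5, 2, 4, 6 h (the protocol gives only under 6 h, for another formulation); ka 1, 2, 4 per hour; lag 0, 15, 30 min; sample 5, 15, 30, 60 min after dose 2; linear and linear-up/log-down trapezoids. That is 4 × 3 × 3 × 4 × 2 = 288 runs. All inputs except the sampling grid are assumptions.

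Multiplier on AUC0-24 by absorption lag and delay from dose 2 to sample:

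| Lag | 5 min | 15 min | 30 min | 60 min |
|---|---|---|---|---|
| 0 | 1.06–1.79 | 1.16–2.67 | 1.27–3.10 | 1.43–2.95 |
| 15 min | 1.00 | 1.00 | 1.16–2.68 | 1.36–3.11 |
| 30 min | 1.00 | 1.00 | 1.00 | 1.28–3.16 |

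Without lag, by half-life: 1.5 h 1.21–3.10; 2 h 1.16–2.64; 4 h 1.08–1.95; 6 h 1.06–1.70. Rac(AUC) without lag is 0.32–1.02 (0.52–1.02 for half-lives of 4 to 6 h), against a true 1.00–1.08.

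Of the 288 runs, 168 raise AUC0-24, 120 leave it unchanged and none lowers it.

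**The case against.** The strongest reply is that the documents nearly settle the order themselves. Section 8.2.1.2.1.2 is explicit, the assessment sections point to it, and the SAP presumes it, so what remains is one stray sentence touching a secondary, descriptive analysis. AUC0-12, AUC0-last as the SAP defines it, and the whole Day 5 profile are untouched. Day 1 Cmax is too, unless the affected sample exceeds the Day 1 peak. Rac(AUC) appears only in the SAP. All of this stands and limits the consequence. It does not let a site follow both instructions.

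The size can also be challenged.

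- With dose 2 exactly at 24 h, the ±30 min window caps the delay at 30 min; 60 min needs an early dose. At delays up to 30 min, 120 of 216 runs show no bias. Without lag and with half-life at least 2 h, the maximum is then 2.64, or 1.91 for 4 to 6 h. The run counts describe a chosen grid and are not probabilities.
- SAP Section 5.4.4 sets terminal and embedded values below the LLOQ to missing for parameter calculation. At half-lives of 1.5 to 2 h the true 24 h concentration in the model is below 0.1% of Cmax and could fall under the LLOQ, which is not given. The largest multipliers may therefore not match the planned calculation. The rule would not remove a quantifiable sample taken after dose 2.

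Finally, Protocol Section 13.1.5.1 defers detail to a separate PK analysis plan, which was not available and may already deal with such samples. That makes the proposed SAP rule conditional; it does not affect the correction to Section 10.3.

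**Conclusion.** The contradiction is real, and Section 10.3 is the sentence to change. Followed as written, it can bias Day 1 AUC0-24 upward and Rac(AUC) downward, never the reverse, and no rule in the two documents removes a single on-time sample drawn after dose 2. The direction rests only on dose-2 drug adding to the 24 h concentration. The size is illustrative: from no bias, when sampling precedes absorption, to roughly a threefold AUC0-24 at the shortest assumed half-life. Without lag, half-lives of 4 to 6 h give 1.06 to 1.95. Whether any subject was affected is unknown, because the documents do not report the order used in Cohorts 1 to 4. Although PK is secondary and descriptive, two dosing instructions that exclude each other should not stay in the protocol when the correction is this cheap.

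**What to change.** 1. Reword Section 10.3: on Day 2 the subject takes the IMP once every 24 h assessment, including the PK draw, is complete, and before leaving hospital. Check the Pharmacy Manual, the administration instructions and the Laboratory Manual, which were not available here, for the same order.
2. Compare recorded Day 2 dose times with 24 h sample times for Cohorts 1 to 4.
3. Unless the separate PK analysis plan already has such a rule, add one to SAP Sections 4.6 and 5.4.4: a 24 h sample recorded after the Day 2 dose is left out of the Day 1 24 h concentration summary; that subject's Day 1 AUC0-24 and Rac(AUC) are set to missing and flagged; all other PK parameters are kept. Setting them to missing is preferred to extrapolation because the SAP lists half-life for Day 5 only. Protocol Section 11.2.3 does derive half-life from each profile, so a plan that prefers extrapolation should say so in advance.

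The cost is one protocol sentence, one SAP rule and a timestamp check. Cohorts 1 to 4 are complete (Protocol Section 13.4), so the protocol edit can change conduct only in Cohort 5; the check and the rule cover the earlier cohorts. The price of the rule is lost AUC0-24 and Rac(AUC) values among 6 active subjects per cohort. At a single centre with one habitual order, that could reach all 5 × 6 = 30.
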